1. KEY STUDY ELEMENTS

1.1. Synopsis

Protocol Title: Escalating Dose and Randomized, Controlled Study of Nusinersen

(BIIB058) in Participants With Spinal Muscular Atrophy

Protocol Number: 232SM203

Version Number: 7

Name of Study

Research Name: BIIB058

Treatment: Generic Name:

Nusinersen

Trade Name:

Spinraza

Study Phase: 2/3

Study Indication: Spinal muscular atrophy (SMA)

Study Rationale: Efficacy and safety results across the nusinersen clinical development

program have demonstrated an overall positive benefit-risk profile of nusinersen across a broad range of SMA phenotypes and patient populations. Nusinersen is approved in the United States, Europe, and other countries and regions for the treatment of SMA in pediatric and adult patients at a recommended dosage of 12 mg administered in

3 loading doses at 14-day intervals, a fourth loading dose 30 days after the third dose, and maintenance doses every 4 months thereafter. Pharmacokinetic (PK) and pharmacodynamic (PD) analyses indicate that nusinersen drug exposure higher than that achieved with 12 mg in patients with SMA may produce an even greater benefit in motor function. Additionally, PK modeling and simulations identified dosing regimens that achieve higher drug exposure more rapidly. Therefore, this study is being conducted to investigate the efficacy, safety, tolerability, of a 50/28-mg dose of nusinersen (50-mg loading dose; 28-mg maintenance dose)

and a dosing regimen targeted to achieve higher drug exposure more rapidly. This study will be conducted in participants with genetically

confirmed SMA.

Rationale for Dose and Schedule Selection:

The clinical PK, safety, and efficacy of nusinersen have been evaluated in a number of patient populations (infantile-onset [SMA symptom onset ≤ 6 months (≤ 180 days) of age], later-onset [SMA

symptom onset > 6 months (> 180 days) of age], and

presymptomatic). The approved dosing regimen of nusinersen is 12 mg administered in 4 loading doses during a 2-month period

followed by maintenance doses every 4 months thereafter. In the original development program, 2 different dosing regimens (4 loading doses followed by maintenance doses every 4 months and 3 loading doses followed by maintenance doses every 6 months) were evaluated in sham-controlled studies. Results from these studies, the population PK and exposure-response modeling, and the nonhuman primate safety studies were used as the basis for selecting dosing regimens in this study.

An exploratory exposure-response analysis performed in participants with infantile-onset SMA (Study CS3A, n = 20, age 38 days to 8 months) showed a statistically significant positive correlation between nusinersen cerebrospinal fluid (CSF) exposure and motor function (e.g., Children's Hospital of Philadelphia Infant Test of Neuromuscular Disorders [CHOP-INTEND] scores).

Previous PK modeling predicted that the median concentration of nusinersen within the CSF immediately prior to the administration of the subsequent maintenance dose (i.e., trough concentration [C_{trough}]) would be approximately 10 ng/mL at steady state with the label-approved maintenance dosing regimen (i.e., 12 mg administered every 4 months) and approximately 20 ng/mL at steady state with the proposed maintenance dosing regimen for Study 232SM203 (i.e., 28 mg administered every 4 months). This model was subsequently updated to include additional data from Studies 232SM201 and CS11 not previously modeled, resulting in an adjustment of CSF C_{trough} predictions in all patient populations, which are still consistent with the prior predictions. As a consequence, population PK modeling now predicts that with increasing the maintenance dose from 12 to 28 mg administered every 4 months. CSF C_{trough} should increase from 5 to 12 ng/mL at steady state. The exposure-response (PK/PD) relationship between steady-state CSF C_{trough} and CHOP-INTEND response continuously increases as a function of PK and is on an upward trajectory at concentrations consistent with the 12 mg maintenance dose (i.e., 5 ng/mL). It is predicted that additional clinical benefit (i.e., a 5-point increase in CHOP-INTEND score) could be achieved by increasing CSF exposures to 12 ng/mL. Therefore, administration of this higher dose of nusinersen may lead to meaningful clinical benefit to patients. At this time, no dose-limiting toxicity has been identified with nusinersen. The PK modeling therefore suggests that it is unlikely that the higher doses of nusinersen would have a less favorable risk-benefit profile compared with standard dose nusinersen.

The PK/PD relationship has thus far been demonstrated primarily in the infantile-onset SMA population. However, the same positive CONFIDENTIAL

PK/PD relationship is expected across SMA types and patient age groups because they share the same disease mechanism. This is supported by the preliminary correlation analysis from Study 232SM202, which showed a positive relationship between CSF C_{trough} and total motor milestones scores in patients with infantile-and later-onset SMA who received 12 mg of nusinersen as 4 loading doses followed by maintenance doses every 4 months.

Using 12 ng/mL as the clinical CSF C_{trough} target concentration and the predicted CSF PK profiles from 28 mg of nusinersen (maintenance doses every 4 months) as the reference dosing regimen, simulations were performed to evaluate additional dosing scenarios with higher doses and reduced loading-dose frequency. Additional evaluation of the maintenance dosing frequency was not performed because previous modeling showed that a dosing frequency of every 4 months best maintained the CSF concentration achieved at steady state.

The assumption of PK linearity is supported by nusinersen toxicokinetic results in nonhuman primates, which showed nearly dose-proportional PK in the plasma and central nervous system tissues (target site of action) up to 15 mg (human equivalent dose of 150 mg). Assuming PK linearity, PK simulations were performed in both infantile- and later-onset SMA populations after 2 years of treatment using a population PK model developed from patients across the age range of ≤ 6 months to 18 years old. Based on the most recent PK modeling performed, relative to the approved 12-mg label regimen (CSF C_{trough} of approximately 5 ng/mL), 28 mg administered as 3 loading doses (biweekly) or 50 mg administered as 2 loading doses (biweekly), each followed by maintenance doses of 28 mg every 4 months, were identified to achieve the desired CSF Ctrough (approximately 12 ng/mL) more rapidly at the end of the loading dose period. Nusinersen 28 mg administered as 3 loading doses (biweekly) had a comparable predicted CSF maximum concentration (C_{max}) to the reference dosing regimen, whereas the 50-mg dosing regimen surpassed the predicted C_{max} from the reference dosing regimen. Moreover, the 28-mg maintenance dosing regimen adequately maintained the higher CSF Ctrough target (approximately 12 ng/mL) during the maintenance dose period. Toxicology studies in nonhuman primates evaluating the nonhuman primate equivalent of the 28- and 50-mg doses have been conducted and support the safety of these doses in a clinical study (see Section 3.3). Therefore, the 28-mg dose (administered as 3 loading doses at biweekly intervals), 50-mg dose (administered as 2 loading doses at biweekly intervals).

and 28-mg maintenance dose were recommended for additional clinical evaluation.

The single bolus dose in Part C is supported by PK simulations showing that a titration dosing regimen of a single loading dose (50 mg) followed by maintenance doses of 28 mg every 4 months thereafter achieved and maintained the higher CSF C_{trough} target concentration (approximately 12 ng/mL) in the representative populations for later-onset and infantile-onset SMA, respectively. The predicted exposures of the proposed titration dosing regimens are covered by the levels demonstrated to be safe in nonhuman primates.

Study Objectives and Endpoints

Part B Primary Objective

To examine the clinical efficacy of nusinersen administered intrathecally at higher doses to participants with SMA in the 232SM203 50/28 mg Group compared to the CS3B Matched Sham Control Group, as measured by change in CHOP-INTEND total score.

Part B Secondary Objectives

To examine the clinical efficacy of nusinersen administered intrathecally at higher doses to participants with SMA in the 232SM203 50/28 mg Group compared to:

• CS3B Matched Sham Control Group

AND

• 232SM203 nusinersen 12 mg Group

Primary Endpoint

Infantile-Onset SMA

 Change from baseline to Day 183 in CHOP-INTEND total score, accounting for mortality/dropout using the joint-rank test (comparison of higher dose to matched sham control)

Secondary Endpoints

Infantile-Onset SMA

- Proportion of Hammersmith Infant Neurological Examination (HINE)
 Section 2 motor milestone responders at Day 183 (comparison of higher dose to matched sham control)
- Change from baseline to Day 183 in HINE Section 2 motor milestones total score (comparison of higher dose to matched sham control)
- Change from baseline to Day 183 in plasma concentration of NF-L (comparison of higher dose to matched sham control)
- Change from baseline to Day 302 in CHOP-INTEND total score

CONFIDENTIAL

The information contained herein may not be used, disclosed, or published without the written consent of Biogen MA Inc.

- (comparison of higher dose to 12 mg dose)
- Change from baseline to Day 302 in HINE Section 2 motor milestones total score (comparison of higher dose to 12 mg dose)
- Change from baseline to Day 29 in plasma concentration of NF-L (comparison of higher dose to 12 mg dose)
- Time to death or permanent ventilation (tracheostomy or ≥ 16 hours of ventilation/day continuously for > 21 days in the absence of an acute reversible event [Appendix A]) (comparison of higher dose to matched sham control)
- Time to death (overall survival) (comparison of higher dose to matched sham control)
- Time to death or permanent ventilation (tracheostomy or ≥ 16 hours of ventilation/day continuously for > 21 days in the absence of an acute reversible event [Appendix A]) (comparison of higher dose to 12 mg dose)
- Time to death (overall survival) (comparison of higher dose to 12 mg dose)

To examine the clinical efficacy of nusinersen administered intrathecally at higher doses compared to the currently approved 12 mg dose in participants with SMA

Later-Onset SMA

- Change from baseline in Hammersmith Functional Motor Scale Expanded (HFMSE) score
- Change from baseline in Revised Upper Limb Module (RULM) score

- Total number of new World Health Organization (WHO) motor milestones
- Change from baseline in Assessment of Caregiver Experience with Neuromuscular Disease (ACEND)
- Change from baseline in Pediatric Quality of Life InventoryTM (PedsQL)
- Change from baseline in CSF concentration of NF-L
- Change from baseline in plasma concentration of NF-L
- Incidence of adverse events (AEs), including serious adverse events (SAEs)
- Shifts from baseline in clinical laboratory parameters, electrocardiograms (ECGs), and vital signs
- Change in growth parameters
- Shifts from baseline in coagulation parameters (activated partial thromboplastin time [aPTT], prothrombin time [PT], and international normalized ratio [INR])
- Change in urine total protein
- Change from baseline in neurological examination outcomes
- The proportion of participants with a postbaseline platelet count below the lower limit of normal on at least
 2 consecutive measurements
- The proportion of participants with a postbaseline corrected QT interval using Fridericia's formula (QTcF) of
 500 msec and an increase from

To examine the safety and tolerability of nusinersen administered intrathecally at higher doses to participants with SMA

To examine the effect of nusinersen administered intrathecally at higher doses compared to the currently approved 12 mg dose in participants

with SMA

baseline to any postbaseline timepoint in QTcF of > 60 msec

Infantile-Onset and Later-Onset SMA

- Number and duration of hospitalizations
- Clinical Global Impression of Change (CGIC) [physician, caregiver] at Day 302
- Number of serious respiratory events
- Proportion of time on ventilation (infantile-onset SMA population)
- Ventilator use
- Change in the Parent Assessment of Swallowing Ability (PASA) scale

Infantile-Onset SMA only

Change from baseline in CSF concentration of NF-L

Parts A and C Primary Objective

To examine the safety and tolerability of nusinersen administered intrathecally at higher doses to participants with SMA

Primary Endpoints

- Incidence of AEs, including SAEs
- Shifts from baseline in clinical laboratory parameters, ECGs, and vital signs
- Change in growth parameters
- Shifts from baseline in coagulation parameters (aPTT, PT, and INR)
- Change in urine total protein
- Change from baseline in neurological examination outcomes
- The proportion of participants with a postbaseline platelet count below the

lower limit of normal on at least 2 consecutive measurements

• The proportion of participants with a postbaseline QTcF of > 500 msec and an increase from baseline to any postbaseline timepoint in QTcF of > 60 msec

Parts A and C Secondary Objectives

To examine the clinical efficacy of nusinersen administered intrathecally at higher doses to participants with SMA

Secondary Endpoints

Parts A and C:

- Change from baseline in HFMSE score
- Change from baseline in RULM score
- Total number of new WHO motor milestones
- Change from baseline in ACEND
- Change from baseline in PedsQL (Part A and Part C Cohort 1 only)

Part C (Cohort 1 only):

- Change from baseline in CHOP-INTEND
- Change from baseline in HINE Section 2 motor milestones

To examine the effect of nusinersen administered intrathecally at higher doses to participants with SMA

Parts A and C:

- Number and duration of hospitalizations
- CGIC (physician, caregiver) at Day 302
- Number of serious respiratory events
- Ventilator use
- Change in the PASA scale (Part A only)

Study Design:

This is a 3-part (Parts A, B, and C) study in which participants will be followed for approximately 10 to 13 months after the first dose of study treatment. Following the completion of this study, all eligible participants may elect to enroll in a separate long-term extension study (232SM302), pending study approval by ethics committees and the appropriate regulatory authorities. In regard to participants rolling over from Part B, this will be done without unblinding the participant's treatment group.

Part A is an open-label safety evaluation. Six participants with later-onset SMA who are 2 to \leq 15 years of age, inclusive, at the signing of informed consent will receive 3 loading doses of 28 mg of nusinersen on Days 1, 15, and 29, followed by 2 maintenance doses of 28 mg on Days 149 and 269. Participants will remain at the clinic for at least 24 hours after each dose. A sentinel dosing approach will be used, in which the first participant will be enrolled and dosed with 28 mg of nusinersen. Following the availability of 72 hours of safety data after the first loading dose in the first participant, data for this participant will be reviewed by the Investigator and the Sponsor before the next 5 participants are enrolled. Only 1 participant can receive their first dose of study treatment on a given day.

After 6 participants have completed the loading period (i.e., when the last participant has available safety data through the Day 64 visit), an independent data monitoring committee (IDMC) will review the available safety data to recommend whether Part B can be initiated. If deemed necessary by the Sponsor, additional participants may be enrolled in Part A to ensure sufficient data are available for the safety evaluation prior to enrollment of participants in Part B. Details regarding the IDMC review of data may be found in the IDMC charter. Meanwhile, participants in Part A will proceed to maintenance dosing without interruption. Note that the IDMC can recommend to stop the study based on the safety findings.

Part B will consist of a pivotal, double-blind, active-controlled treatment period with either 2 or 4 loading doses of nusinersen (for the 50/28-mg and Control Groups, respectively) administered intrathecally followed by maintenance doses approximately every 4 months thereafter. Approximately 99 participants with infantile- or later-onset SMA will be randomized in a 1:2 ratio to receive either the currently approved dosing regimen of 4 loading doses of 12 mg of nusinersen administered intrathecally (Days 1, 15, 29, and 64) followed by 2 maintenance doses of 12 mg on Days 183 and 279 (Control Group) or 2 loading doses of 50 mg of nusinersen administered intrathecally (Days 1 and 15) followed by

2 maintenance doses of 28 mg on Days 135 and 279 (50/28-mg Group). In order to maintain blinding, 1 sham procedure will be administered in the Control Group on Day 135 and 3 sham procedures will be administered in the 50/28-mg Group on Days 29, 64, and 183 to ensure the same dosing visit schedule as the Control Group. Participants will remain at the clinic for at least 24 hours after study treatment administration on Days 1 and 15; inpatient stays at other visits may occur based on the Investigator's discretion. If the primary reason for the inpatient stay is due to an AE or SAE, reporting requirements per Section 11.3 must be followed.

Once the fifteenth participant in Part B has been enrolled and administered the first dose of study treatment, no new participants will be dosed in Part B until after an IDMC review. The IDMC will review unblinded data from the first 15 participants in Part B who have completed the Day 29 visit (in order to achieve 6 or more participants who have received 50 mg in the 50/28-mg Group, while maintaining the blind for the rest of the study team). This review will include safety data through the Day 29 visit at a minimum and all available individual CSF and plasma nusinersen concentration data for these participants, including the Day 15 samples at a minimum. Dosing of the remaining participants in Part B and dosing in Part C will occur only after this review has completed, provided that no safety concerns are identified. Note that the IDMC can recommend to stop the study based on the safety findings. By the time of implementation of Protocol Version 6, the IDMC reviewed these data and recommended that the study may continue with dosing of the remaining participants in Part B and initiating dosing in Part C without any modifications to the study.

In Part C, up to approximately 40 participants who have already initiated treatment with nusinersen and have been receiving the approved dose of 12 mg for at least 1 year prior to entry will be enrolled. The initial cohort in Part C (i.e., Cohort 1) consists of up to approximately 20 participants of any age or SMA status. For Cohort 1, an attempt will be made to enroll at least 8 but no more than 12 participants \geq 18 years of age (participants in Cohort $1 \geq$ 18 years of age must be ambulatory). Up to 5 participants with severe scoliosis and/or severe contractures may be enrolled in Cohort 1 of Part C after consultation with the Medical Monitor. An additional cohort (i.e., Cohort 2) consisting of up to approximately 20 adult participants (\geq 18 years of age) was subsequently added to Part C in Protocol Version 5 in order to enable collection of data in adults transitioning from the currently approved nusinersen dosing regimen to higher

dose. Participants in Cohort 2 can be either ambulatory on nonambulatory.

All participants in Part C will receive a single bolus dose of 50 mg (which should be administered 4 months \pm 14 days after their most recent maintenance dose of 12 mg) followed by 2 maintenance doses of 28 mg on Days 121 and 241. Participants in Part C will remain at the clinic for at least 24 hours after the first (bolus) dose for the purpose of completing study assessments.

Study Location: Approximately 65 sites globally are planned.

Study Population: This study will be conducted in participants who meet the following criteria:

• Parts A, B, and C:

 Genetic documentation of 5q SMA (homozygous gene deletion, mutation, or compound heterozygote)

• Part A:

Participants with later-onset SMA, aged 2 to
 ≤ 15 years, inclusive, at the time of informed consent

• Part B:

- Participants with infantile-onset SMA, aged > 1 week to ≤ 7 months (≤ 210 days) at the time of informed consent
- Participants with later-onset SMA, aged 2 to
 10 years at the time of informed consent

Part C:

Cohort 1:

- Males and females of any age (individuals ≥ 18 years of age at Screening must be ambulatory)
- Have been receiving treatment with nusinersen for at least 1 year prior to entry in this study

Cohort 2:

- Males and females ≥ 18 years of age (can be ambulatory or nonambulatory)
- Have been receiving treatment with nusinersen for at least 1 year prior to entry in this study

Detailed criteria are described in Section 6.

Number of Planned Participants:

Including all 3 parts (A, B, and C), approximately 145 participants may be enrolled.

Treatment Groups:

• Part A: Six participants with later-onset SMA will receive 3 loading doses of 28 mg of nusinersen administered intrathecally on Days 1, 15, and 29. Maintenance doses of 28 mg of nusinersen will be administered on Days 149 and 269.

Part B:

- Control Group: A total of 33 participants (25 with infantile-onset SMA and 8 with later-onset SMA) will receive 4 loading doses of 12 mg of nusinersen administered intrathecally (Days 1, 15, 29, and 64), followed by maintenance doses of 12 mg on Days 183 and 279 (and a sham procedure on Day 135).
- 50/28-mg Group: A total of 66 participants (50 with infantile-onset SMA and 16 with later-onset SMA) will receive 2 loading doses of 50 mg of nusinersen administered intrathecally (Days 1 and 15) and 2 sham procedures on Days 29 and 64, followed by maintenance doses of 28 mg on Days 135 and 279 (and a sham procedure on Day 183).
- Part C: Up to approximately 40 participants (i.e., up to approximately 20 participants each in Cohorts 1 and 2) who have already been receiving treatment with nusinersen for at least 1 year prior to entry in this study will receive a single bolus dose of 50 mg of nusinersen administered intrathecally on Day 1 in this study (which should be administered 4 months ± 14 days after their most recent maintenance dose of 12 mg), followed by 2 maintenance doses of 28 mg of nusinersen on Days 121 and 241.

Sample Size Determination:

A total sample size of approximately 145 participants is planned for this study (Table 9). The justification for the sample size for the infantile-onset SMA population in Part B is detailed below. The sample sizes for the remaining groups are not based on statistical considerations.

A minimum of 6 participants with later-onset SMA will be enrolled in Part A to characterize the safety, tolerability. of a 28/28 mg dose of nusinersen (28-mg loading dose; 28-mg maintenance dose). A total of 24 participants with later-onset SMA will be randomized to the Control Group and 50/28-mg Group in Part B in a ratio of 1:2; this will allow the exploration of the safety, tolerability, and efficacy of a 50/28 mg dose of nusinersen in this population. A total of up to approximately 40 participants will be enrolled in Part C (i.e., up to approximately 20 participants each in Cohorts 1 and 2) to characterize the safety, tolerability, of a 50/28-mg dose of nusinersen in participants transitioning from maintenance dosing at the currently approved dose of 12 mg of nusinersen.

For the infantile-onset SMA population in Part B, a sample size of approximately 50 participants in the 50/28-mg Group and a minimum of N=20 sham participants will provide at least approximately 99% power for the primary endpoint to detect an improvement of 24 points on CHOP-INTEND and 23% survival rate benefit (compared to that observed in Study CS3B participants receiving sham control) at Day 183 based on the joint-rank test at a 2-sided significance level of 0.05. This power calculation is based on simulations using data generated from a joint model of survival and functional change. The model used a difference of 24 points for the Day 183 change from baseline in CHOP-INTEND total score (50/28-mg Group – Study CS3B Sham Control Group) and a population standard deviation of 8.8 for change from baseline.

For Part B, the randomization will be stratified as follows:

- For participants with infantile-onset SMA by disease duration: ≤ 12 weeks and > 12 weeks (time from age at symptom onset to age at informed consent)
- For participants with later-onset SMA by age at informed consent: < 6 years and ≥ 6 years

Visit Schedule:

Participants will have up to 10 visits during the study. The number of visits for each part is as follows:

• Part A: 8 to 9 visits

• Part B: 9 to 10 visits

• Part C: 5 to 6 visits

Visits during Days 1, 15, and 29 of the loading periods of Parts A and B, and Day 1 of the loading period of Part C should be performed \pm 1 day from the nominal visit day. Visits during Day 64 of the loading period of Parts A and B and the maintenance period of Parts A, B, and C should be performed \pm 7 days from the nominal visit day. Visit days are calculated with respect to Day 1 (the date of first dose).

Study assessments conducted at each visit are listed in the Schedule of Activities (Table 1, Table 2, Table 3, and Table 4).

Duration of Study Participation:

Study duration for each participant will be as follows:

Part A: approximately 323 to 410 days

• Screening: 21 days

• Loading period: 64 days

• Maintenance period: 205 days

• Follow-up: 33 to 120 days

Part B: approximately 323 to 420 days

• Screening: 21 days

• Loading period: 64 days

• Maintenance period: 215 days

• Follow-up: 23 to 120 days

Part C: approximately 323 to 382 days

• Screening: 21 days

• Loading period: 1 day

• Maintenance period: 240 days

Follow-up: 61 to 120 days

Benefit-Risk Analysis:

Nusinersen (Spinraza) 12 mg has a positive benefit-risk profile, with more than 4 years of postmarketing experience and more than 11,000 patients treated. The safety profile to date does not preclude study of higher doses in any population.

Detailed information about the known and expected benefits and risks, reasonably expected AEs, and nonclinical toxicology studies supporting investigation of higher doses of nusinersen in the clinic are provided in the Investigator's Brochure and informed consent form. A high-level summary of the benefits and risks known during study design is provided here.

[figure not shown]
Anticipating a potential enhancement of benefit with the dosing regimens proposed for Study 232SM203, substantiated by PK/PD modeling described in Section 3.1.2, the safety of the loading period for Study 232SM203 is supported by a nonclinical study conducted in monkeys (Study P058-17-03). In this study, the no-observed-adverse-effect level (NOAEL) was 15 mg (human equivalent dose of 150 mg). As such, dosing for Study 232SM203 has a safety margin of at least 4.5-fold for cumulative doses during the loading period and a 3-fold margin for a single loading dose of 50 mg.

The safety of long-term exposure during the Study 232SM203 maintenance period is supported by a 53-week monkey study (Study 396443-AS06). Monkeys received a cumulative dose of 3.9, 13, and 52 mg at each dose level (0.3, 1, and 4 mg per dose, respectively) during the 52-week treatment duration. The overall NOAEL was determined to be 4 mg. Tissue concentrations measured in monkeys from the 53-week toxicology study at the NOAEL (4 mg) were compared to the estimated tissue concentrations in patients with SMA. The exposure-based safety margin is at least 1.4-fold based on exposure in the spinal cord (safety margins are higher for other tissues).

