12.3. Definition of Baseline

The baseline for all assessments except CHOP-INTEND is defined as the last nonmissing assessment prior to the first dose of study treatment. The baseline for CHOP-INTEND is defined as the average of the assessments taken during the Screening/Baseline period.

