12.8.3. Vital Signs

The analysis of vital signs will focus on clinically significant abnormalities. Changes from baseline in vital signs and ECGs will be summarized.

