12.11. Sample Size Considerations

A total sample size of approximately 145 participants is planned for this study (Table 9). The justification for the sample size for the infantile-onset SMA population in Part B is detailed as follows. The sample sizes for the remaining groups are not based on statistical considerations.

A minimum of 6 participants with later-onset SMA will be enrolled in Part A to characterize the safety, tolerability, and of a 28/28-mg dose of nusinersen (28-mg loading dose; 28mg maintenance dose). A total of 24 participants with later-onset SMA will be randomized to the Control Group and 50/28-mg Group in Part B in a ratio of 1:2; this will allow the exploration of the safety, tolerability, and efficacy of the 50/28 mg dose of nusinersen in this population. A total of up to approximately 40 participants will be enrolled in Part C (i.e., up to approximately 20 participants each in Cohorts 1 and 2) to characterize the safety, tolerability, and of a 50/28 mg dose of nusinersen in participants transitioning from maintenance dosing at the currently approved dose of 12 mg of nusinersen.

Table 9: Number of Participants in Each Study Part, by Symptom Onset

Part/Dose	Number of Participants		
	Later Onset	Infantile Onset	Total
Part A (28-mg loading dose; 28-mg maintenance dose)	6		6
Part B			
Control Group (12-mg loading dose; 12-mg maintenance dose)	8	25	33
50/28-mg Group (50-mg loading dose; 28-mg maintenance dose)	16	50	66
Part C (50-mg loading dose; 28-mg maintenance dose)			401
Total			145 ¹

The sample size is an estimate that may be up to approximately the stated number.

For the infantile-onset SMA population in Part B, a sample size of approximately 50 participants in the 50/28-mg Group and at least N= 20 sham participants from CS3B will provide at least approximately 99% power for the primary endpoint to detect an improvement of 24 points on CHOP-INTEND and 23% survival rate benefit (compared to that observed in Study CS3B participants receiving sham control) at Day 183 based on the joint-rank test at a 2-sided significance level of 0.05. This power calculation is based on simulations using data generated from a joint model of survival and functional change. The model used a difference of 24 points for the Day 183 change from baseline in CHOP-INTEND total score (50/28-mg Group — Study CS3B Sham Control Group) and a population standard deviation of 8.8 for change from baseline.

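### The QTcF safety endpoint is one proportion requiring both a value above 500 msec and a rise above 60 msec, so a participant who passes only one threshold is not counted

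*Protocol*

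**What the plan says.** In the Synopsis (Section 1.1), the primary endpoints for Parts A and C include a single proportion, defined by this joint condition: "postbaseline QTcF of > 500 msec and an increase from baseline to any postbaseline timepoint in QTcF of > 60 msec". The Part B safety list in the Synopsis uses the same joining word ("500 msec and an increase from"). Section 4 repeats the definition twice, once for Part B and once for Parts A and C. Nowhere does the current text use the word or between the two limits, or give either limit its own proportion.

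Section 12.3 sets the reference value: "The baseline for all assessments except CHOP-INTEND is defined as the last nonmissing assessment prior to the first dose of study treatment".

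Two other provisions deal with ECG data. One is an endpoint, "Shifts from baseline in clinical laboratory parameters, ECGs, and vital signs"; the other is the planned summary in Section 12.8.3, "Changes from baseline in vital signs and ECGs will be summarized". Neither names a QTcF limit.

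On size, Section 12.11 says "A minimum of 6 participants with later-onset SMA will be enrolled in Part A" and "A total of up to approximately 40 participants will be enrolled in Part C", and adds that "The sample sizes for the remaining groups are not based on statistical considerations".

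**The concern.** An absolute QTcF above 500 msec and a rise above 60 msec are different conditions, and joining them reports only their overlap. A participant who goes from 400 to 495 msec has risen by 95 msec and is not an event. A participant who goes from 445 to 502 msec has passed 500 msec and is not an event either, because the rise is 57 msec.

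Safety is the primary objective of Parts A and C, and the doses are above the approved 12 mg. No hypothesis test is attached to this endpoint, so the count itself is the result. If the count leaves out participants who pass one limit, a reader of the results can take a low or zero figure as reassurance that the definition does not support.

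**Working it through.** **No stated figure to reproduce.** The protocol attaches no expected rate, power or sample size to this endpoint.

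**Step 1: exact arithmetic, no assumptions.** Each participant has one baseline B, so the highest postbaseline value decides both conditions, whichever visit it comes from. With R the largest rise, the participant is counted only if R > 60 and B + R > 500, that is, R > max(60, 500 - B).

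| Baseline B (msec) | 500 - B | Rise needed to be counted |
|---|---|---|
| 380 | 120 | > 120 |
| 400 | 100 | > 100 |
| 420 | 80 | > 80 |
| 430 | 70 | > 70 |
| 440 | 60 | > 60 |
| 445 | 55 | > 60 |

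Below 440 the absolute limit binds, and rises between 60 and 500 - B are lost. Above 440 the rise limit binds, and values above 500 msec reached by a rise of 60 or less are lost. At 445, for example, the lost values lie above 500 and up to 505 msec.

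**Step 2: size, under assumptions that are not in the documents.** Baseline QTcF is taken as normal with mean 390 to 450 and SD 15, 20 or 25 msec. The change is taken as normal with mean/SD of 10/20, 20/25 or 30/30 msec, independent of baseline. The share of rises above 60 msec that the joint rule captures is P(both) / P(rise > 60). The share of all participants passing a limit is P(both) / P(either).

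| Mean baseline | Share of rises > 60 captured |
|---|---|
| 390-410 | 0.5-30% |
| 420 | 19-43% |
| 430 | 41-59% |
| 440 | 59-78% |
| 450 | 74-91% |

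As a share of participants meeting either condition, the joint rule captures 0.5-38% at mean baselines 390-420 and 4-56% at 430-450. At the higher baselines it recovers more of the large rises but loses more of the values above 500 msec.

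**Step 3: sensitivity to independence.** With a correlation of -0.4 between baseline and change (baseline SD 20; change 20, SD 25), the share of rises above 60 msec captured falls to 1% at mean baseline 400, 9% at 420 and 38% at 440.

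**Step 4: what a report might show.** With baseline 400 (SD 20) and change 20 (SD 25), 5.5% of participants rise by more than 60 msec, 5.6% meet either condition and 0.5% meet both. For 40 participants in Part C, the chance of no event at all is 0.995^40 = 0.82 for the joint rule and 0.944^40 = 0.10 for either.

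**The case against.** The wording is consistent at every occurrence, and a strict joint criterion, less sensitive but more specific, can be a deliberate choice. The second condition carries its own time phrase, so the line might also be a compressed list of two criteria. That reading is possible, but the text states one proportion and never says otherwise. If two were meant, the line still needs correcting.

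Other provisions see ECG changes. ECG shifts are a listed endpoint, and ECG changes are summarized. Under Section 11.1.1 an ECG result that the investigator judges clinically significant is an adverse event, and adverse event incidence is itself a primary endpoint in Parts A and C. The IDMC reviews safety data from Part A and from the first 15 participants in Part B. This stands as mitigation: the data are collected and a large average effect would be visible. None of these provisions states a QTcF limit, so none replaces a count of participants beyond one.

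The analysis plan may tabulate each limit alone. That would help, but it would not alter a primary endpoint that the protocol itself defines.

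The gain also depends on the effect assumed. With a change of mean 10 and SD 20, P(rise > 60) = 0.62%, or 46 x 0.0062 = 0.3 participants in Parts A and C together, so a separate count would probably read zero too. With mean 20 and SD 25 it is 46 x 0.055 = 2.5 participants.

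**Conclusion.** The definition should be corrected. That a participant passing one limit alone is not counted follows from the wording and holds at every baseline other than exactly 440 msec, where the two limits coincide.

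The size of the loss is not fixed by the documents, because no baseline QTcF is given. Under the assumptions above, more than half of rises over 60 msec are missed for mean baselines up to about 420 msec, about half at 430 and fewer than half at 440 or more; a negative correlation between baseline and change makes the loss larger. In every independent setting examined, the joint rule captures at most 56% of participants meeting either condition.

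A reader might infer that the endpoint misses most large prolongations, or captures only about a tenth of outliers. That needs a low baseline or a large average rise: for example, baseline 400 (SD 15) with a mean rise of 40 (SD 25) gives 21% above +60 msec and 2.0% meeting both. Nothing in the protocol gives that baseline or predicts such a rise, and at mean baselines of 440-450 with independent changes the rule captures 59-91% of rises above 60 msec. Nor do the documents support the reading that a QT signal would go unseen, given the other ECG and adverse event reporting. The point concerns how the endpoint is defined and reported, not clinical management.

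**What to change.** In the Synopsis (Part B safety list, and Parts A and C primary endpoints) and at both places in Section 4, replace the single proportion with separate ones: (a) any postbaseline QTcF above 500 msec; (b) any increase from baseline above 60 msec; (c) either. The joint proportion can stay as an optional further row. The cost is wording and a few table rows. The scheduled ECGs already supply the data, and no sample size or test changes.
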